5.2 Contraception Recommendations

Contraception Requirements for Females

Subjects must follow the following contraceptive guidelines as specified:

- Females, Nonchildbearing Potential

Females do not need to use birth control during or following study drug treatment if considered of nonchildbearing potential due to meeting any of the following criteria:

1. Premenopausal female with permanent sterility or permanent infertility due to one of the following:
 - Permanent sterility due to a hysterectomy, bilateral salpingectomy, bilateral oophorectomy
 - Nonsurgical permanent infertility due to Mullerian agenesis, androgen insensitivity, or gonadal dysgenesis; investigator discretion should be applied to determining study entry for these individuals.
2. Postmenopausal female
 - Age \leq 55 years with no menses for 12 or more months without an alternative medical cause

- Females, of Childbearing Potential
 - Females of childbearing potential must avoid pregnancy while taking study drug(s) and for at least 30 days after the last dose of study drug.
 - Females must commit to one of the following methods of birth control:
 - Combined (estrogen and progestogen containing) hormonal birth control (oral, intravaginal, transdermal, injectable) associated with inhibition of ovulation-initiated at least 30 days prior to study Baseline Day 1
 - Progestogen-only hormonal birth control (oral, injectable, implantable) associated with inhibition of ovulation initiated at least 30 days prior to study Baseline Day 1
 - Bilateral tubal occlusion/ligation (can be via hysteroscopy, provided a hysterosalpingogram confirms success of the procedure)
 - Intrauterine device
 - Intrauterine hormone-releasing system
 - Vasectomized partner (provided the partner has received medical confirmation of the surgical success of the vasectomy and is the sole sexual partner of the trial subject)
 - Practice true abstinence, defined as: refraining from heterosexual intercourse when this is in line with the preferred and usual lifestyle of the subject (periodic abstinence)

[e.g., calendar, ovulation, symptothermal, post-ovulation methods] and withdrawal are not acceptable)

- Progestogen-only oral hormonal contraception, where inhibition of ovulation is not the primary mode of action, initiated at least 30 days prior to Study Day 1
- Male or female condom with or without spermicide
- Cap, diaphragm, or sponge with spermicide
- A combination of male condom with cap, diaphragm, or sponge with spermicide (double-barrier method)

5.3 Prohibited Medications and Therapy

During the study, the following are prohibited.

- Use of medications that may have a substantial effect on visual function or the optical properties of the eye is prohibited 2 weeks prior to the Day 1 visit and during the study:
 - Systemic medications with potential ocular side effects, including topiramate, hydroxychloroquine, ethambutol, phosphodiesterase 5 inhibitors (sildenafil, vardenafil, tadalafil), or tamoxifen
 - Ophthalmic, systemic, or intranasal anticholinergics and α -adrenergic receptor agonists with potential pupillary or accommodative effects, including oxymetazoline, tetrahydrozoline, phenylephrine, naphazoline, cyclopentolate, atropine
 - Cholinergic agonists such as pilocarpine, carbachol, and aceclidine
 - Alpha adrenergic antagonists including phentolamine mesylate
 - Tricyclic antidepressants
- Use of systemic antihistamines (including those used in over-the-counter (OTC) cold and flu preparations) is prohibited within 3 days prior to a study visit and on visit days.
- Use of selective serotonin and serotonin-norepinephrine reuptake inhibitors (SSRIs and SNRIs) is not prohibited if dosage is consistent for at least 30 days prior to randomization and throughout the study.
- Use of ocular medications other than the study drug or medications administered to conduct study procedures is prohibited from the screening visit until study exit.

The decision to administer a prohibited medication/treatment will be made with the safety of the study subject as the primary consideration. When possible, AbbVie should be notified before the prohibited medication/treatment is administered.

5.4 Prior and Concomitant Therapy

Any medication or vaccine (including OTC or prescription medicines, vitamins, and/or herbal supplements) that the subject is receiving at the time of enrollment or receives during the study must be recorded through study exit.

Any questions regarding concomitant or prior therapy should be raised to the AbbVie emergency contact. Information regarding potential drug interactions with AGN-190584 can be located in the AGN-190584 IB.

Subjects must be able to safely discontinue any prohibited medications as described in the Eligibility Criteria (Section 5.1) and Prohibited Medications and Therapy (Section 5.3). Subjects must be consented for the study prior to discontinuing any prohibited medications for the purpose of meeting study eligibility.

COVID-19 Pandemic-related Vaccination Guidance

Given the ongoing COVID-19 pandemic, selected vaccines (e.g., messenger ribonucleic acid, nonreplicating viral vector, protein subunit, etc.) to prevent SARS-CoV-2 infection may be administered during screening or the treatment period, as long as components of the vaccine are not contraindicated.

The decision to receive a locally available vaccine should be based on local guidance and an individual discussion between the treating physician and the subject.

The potential impact of AGN-190584 on SARS-CoV-2 vaccination is unknown. Therefore, study drug should be administered as follows:

- The first dose of AGN-190584, when possible, is preferred to be given at least \pm 14 days from the final SARS-CoV-2 vaccine administration.

Note: The above guidance applies to all SARS-CoV-2 vaccine doses given as part of the complete vaccination course.

These recommendations may be subject to change based on the evolving knowledge around the use of SARS-CoV-2 vaccines in subjects with presbyopia and as more data are collected in real-world scenarios and clinical trials.

Any SARS-CoV-2 vaccine information must be documented on the COVID-19 vaccine electronic case report form. Refer to the Operations Manual for instructions on reporting any AEs associated with the COVID-19 vaccine.

5.5 Withdrawal of Subjects and Discontinuation of Study

A subject may voluntarily withdraw or be withdrawn from the study at any time for reasons including, but not limited to, the following:

- Clinically significant AEs, which rule out continuation of the study drug, as determined by the investigator or the AbbVie Therapeutic Area Medical Director
- The investigator believes it is in the best interest of the subject.
- The subject requests withdrawal from the study.
- Eligibility criteria violation was noted after the subject started study drug and continuation of the study drug would place the subject at risk.
- Introduction of prohibited medications or dosages and continuation of the study drug would place the subject at risk.
- The subject becomes pregnant while on study drug.
- Subject is significantly noncompliant with study procedures, which would put the subject at risk for continued participation in the trial.

For subjects to be considered lost to follow-up, reasonable attempts must be made to obtain information on the subject's final status. At a minimum, 2 telephone calls must be made and 1 certified letter must be sent and documented in the subject's source documentation.

AbbVie may terminate this study prematurely, either in its entirety or at any site. The investigator may also stop the study at his/her site if he/she has safety concerns. If AbbVie terminates the study for safety reasons, AbbVie will promptly notify the investigator.

COVID-19 Pandemic-related Acceptable Protocol Modification

During the COVID-19 pandemic, it has been necessary to employ mitigation strategies to enable the investigator to ensure subject safety and continuity of care. Acceptable mitigation strategies are identified and included in the Operations Manual in [Appendix F](#).

The investigator should contact the sponsor medical contact before discontinuing a subject from the study for a reason other than described in the protocol to ensure all acceptable mitigation steps have been explored.

Interruption/Discontinuation of Study Drug Due to COVID-19 Infection

During the study drug dosing period, a subject with confirmed (viral test positive) or suspected COVID-19 infection will be discontinued. Follow subsequent protocol Section [5.6](#) for subjects who discontinue study drug.

5.6 Follow-Up After Subject Discontinuation of Study Drug or from Study

Subjects who prematurely discontinue study drug treatment will be encouraged to stay in the study for safety assessments, unless subjects have decided to discontinue the study participation entirely (withdrawal of informed consent). Subjects should be advised on the continued scientific importance of their data even if they discontinue treatment with study drug early.

If a subject prematurely discontinues study participation (withdrawal of informed consent), the procedures outlined for the Premature Discontinuation visit should be completed as soon as possible, preferably within 2 weeks.

5.7 Study Drug

AGN-190584 or matching vehicle manufactured by AbbVie will be administered bilaterally twice daily beginning on Day 1 (Baseline) and should be taken at approximately the same time each day (6 hours apart). On the day before office visits, the study drug must be administered no less than 12 hours before the scheduled visit time. The study site personnel will document compliance and any missed doses should be reported to the investigator by the subject.

The subject will be instructed to return all drug containers (even if empty) to the study site personnel at each study visit.

AbbVie will provide study drug for AGN-190584 or matching vehicle. AbbVie-provided study drug should not be substituted or alternately sourced unless otherwise directed by AbbVie.

AGN-190584 and matching vehicle will be packaged in bottles with quantities sufficient to accommodate the study design. Each kit will be labeled per local requirements and this label must remain affixed to the kit. Upon receipt, study drug should be stored as specified on the label and kept in a secure location. Each kit will contain a unique kit number. This kit number is assigned to a subject via interactive response technology (IRT) and encodes the appropriate study drug to be dispensed at the subject's corresponding study visit. Site staff will complete all blank spaces on the label before dispensing to subjects. Study drug will only be used for the conduct of this study.

Table 3. Study Drug Identification

	Investigational Product	Investigational Product Vehicle
Investigational product name	AGN-190584	Vehicle
Active ingredient	Pilocarpine HCl 1.25%	Not applicable
Mode/Route of administration (ROA)	Topical eyedrop	Topical eyedrop
Formulation	Pilocarpine HCl 1.25% Ophthalmic Solution (011430X) Lot T1484 Manufactured at Allergan Sales, LLC	Oxymetazoline HCl and Pilocarpine HCl Placebo Ophthalmic Solution (11258X) Lot T1469 Manufactured at Allergan Sales, LLC
Dosage form	Topical eyedrop	Topical eyedrop
Dose and units	1 drop in each eye twice daily	1 drop in each eye twice daily
Drug preparation/packaging	Study drug will be provided in sterile, 5 mL bottles in a carton. Each bottle & carton will be labeled as required per country requirement.	Study drug will be provided in sterile, 5 mL bottles in a carton. Each bottle & carton will be labeled as required per country requirement.
Masking	Masked	Masked
Frequency of administration	Twice daily to each eye, 6 hours apart	Twice daily to each eye, 6 hours apart
Volume of study drug	3.5 mL per bottle	3.5 mL per bottle
Storage conditions	In a refrigerator, refrigerated: 2°C to 8°C	In a refrigerator, refrigerated: 2°C to 8°C

5.8 Randomization/Drug Assignment

All subjects will be assigned a unique identification number by the IRT at the screening visit. For subjects who rescreen, a new screening number will be assigned by the IRT. The IRT will assign a randomization number that will encode the subject's treatment group assignment according to the randomization schedule.

Subjects will be randomized in a 1:1 ratio to receive either AGN-190584 or vehicle dosed twice daily, in each eye, for 14 days.

Randomization will be further stratified by the following stratification factors:

- Age group: ≤ 50 years and > 50 years
- Baseline binocular mesopic DCNVA severity: 20/63 or better, and worse than 20/63; with a maximum of 50% enrolled subjects with baseline binocular mesopic DCNVA of 20/63 or better

- Iris color: brown and nonbrown
- Emmetrope status: emmetrope and nonemmetrope; with a maximum of 25% enrolled subjects with nonemmetrope. A subject will be considered as emmetrope if both eyes of the subject satisfy the 2 criteria: 1) -0.5D to +0.75D in sphere, inclusively; and 2) $\leq 0.75D$ in Cylinder.

All AbbVie personnel with direct oversight of the conduct and management of the study (with the exception of the AbbVie Drug Supply Management Team), the investigator, study site personnel, and the subject will remain masked to each subject's treatment throughout the study. To maintain the masking, the AGN-190584 and vehicle containers provided for the study will be identical in appearance. The IRT will provide access to unmasking subject treatment information in the case of a medical emergency.

5.9 Protocol Deviations

AbbVie does not allow intentional/prospective deviations from the protocol except when necessary to eliminate an immediate hazard to study subjects. The investigator is responsible for complying with all protocol requirements, written instructions, and applicable laws regarding protocol deviations. If a protocol deviation occurs (or is identified, including those that may be due to the COVID-19 pandemic), the investigator is responsible for notifying the IRB, regulatory authorities (as applicable), and AbbVie.

6 SAFETY CONSIDERATIONS

6.1 Complaints and Adverse Events

Complaints

A complaint is any written, electronic, or oral communication that alleges deficiencies related to the physical characteristics, identity, quality, purity, potency, durability, reliability, safety, effectiveness, or performance of a product/device. Complaints associated with any component of this investigational product must be reported to AbbVie.

Product Complaint

A product complaint is any complaint related to the biologic or drug component of the product or to the medical device component(s).

For a product this may include, but is not limited to, damaged/broken product or packaging, product appearance whose color/markings do not match the labeling, labeling discrepancies/inadequacies in the labeling/instructions (e.g., printing illegible), missing components/product, device damage or not working properly, or packaging issues.

Product complaints concerning the investigational product and/or device must be reported to AbbVie within 24 hours of the study site's knowledge of the event. Product complaints occurring during the study will be followed up to a satisfactory conclusion.

Medical Complaints/Adverse Events and Serious Adverse Events: AGN-190584

An AE is defined as any untoward medical occurrence in a subject or clinical investigation subject administered a pharmaceutical product and which does not necessarily have a causal relationship with this treatment. An AE can therefore be any unfavorable and unintended sign (including an abnormal laboratory finding), symptom, or disease temporally associated with the use of a medicinal (investigational) product, whether or not the event is considered causally related to the use of the product.

Such an event can result from use of the drug as stipulated in the protocol or labeling, as well as from "special situations" such as accidental or intentional overdose, medication error, occupational or accidental exposure, off-label use, drug abuse, drug misuse, or drug withdrawal, all which must be reported whether associated with an AE or not. Any worsening of a pre-existing condition or illness is considered an AE. Worsening in severity of a reported AE should be reported as a new AE. Changes in vital signs are considered to be AEs only if they result in discontinuation from the study, necessitate therapeutic medical drug, and/or if the investigator considers them to be AEs.

The investigators will monitor each subject for clinical evidence of AEs on a routine basis throughout the study. All AEs will be followed to a satisfactory conclusion.

An elective surgery/procedure scheduled to occur during a study will not be considered an AE if the surgery/procedure is being performed for a pre-existing condition and/or the surgery/procedure has been pre-planned prior to study entry. However, if the pre-existing condition deteriorates unexpectedly during the study (e.g., surgery performed earlier than planned), then the deterioration of the condition for which the elective surgery/procedure is being done will be considered an AE.

If an AE, whether associated with study drug or not, meets any of the following criteria, it is to be reported to AbbVie clinical pharmacovigilance or contract research organization (as appropriate) as a Serious adverse event (SAE) within 24 hours of the site being made aware of the SAE (refer to Section 4.3 of the Operations Manual for reporting details and contact information):

Death of Subject	An event that results in the death of a subject
Life-threatening	An event that, in the opinion of the investigator, would have resulted in immediate fatality if medical drug had not been taken. This does not include an event that would have been fatal if it had occurred in a more severe form.
Hospitalization or Prolongation of Hospitalization	An event that results in an admission to the hospital for any length of time or prolongs the subject's hospital stay. This does not include an emergency room visit or admission to an outpatient facility.
Congenital Anomaly	An anomaly detected at or after birth, or any anomaly that results in fetal loss

Persistent or Significant Disability/Incapacity	An event that results in a condition that substantially interferes with the activities of daily living of a study subject. Disability is not intended to include experiences of relatively minor medical significance such as headache, nausea, vomiting, diarrhea, influenza, and accidental trauma (e.g., sprained ankle).
Important Medical Event Requiring Medical or Surgical Drug to Prevent Serious Outcome	An important medical event that may not be immediately life-threatening or result in death or hospitalization but, based on medical judgment, may jeopardize the subject and may require medical or surgical drug to prevent any of the outcomes listed above (i.e., death of subject, life threatening, hospitalization, prolongation of hospitalization, congenital anomaly, or persistent or significant disability/incapacity). Additionally, any elective or spontaneous abortion or stillbirth is considered an important medical event along with any suspected transmission of an infectious agent via a medicinal product if no other serious criterion is applicable. Examples of such events include allergic bronchospasm requiring intensive treatment in an emergency room or at home, blood dyscrasias or convulsions that do not result in inpatient hospitalization, or the development of drug dependency or drug abuse.

All adverse events, whether solicited or spontaneously reported by the subject, will be collected from the time of study drug administration through study exit, unless spontaneously report after study exit. In addition, study procedure-related serious and nonserious adverse events will be collected from the time the subject signs the study-specific informed consent.

The following definitions will be used for serious adverse reaction (SAR) and suspected unexpected serious adverse reaction (SUSAR):

SAR	Defined as all noxious and unintended responses to an investigational medicinal product (IMP) related to any dose administered that result in an SAE as defined above
SUSAR	Refers to individual SAE case reports from clinical trials where a causal relationship between the SAE and the IMP was suspected by either the sponsor or the investigator, is unexpected (not listed in the applicable reference safety information), and meets one of the above serious criteria

AbbVie will be responsible for SUSAR reporting for the IMP in accordance with global and local requirements.

Adverse events will be monitored throughout the study to identify any of special interest that may indicate a trend or risk to subjects.

Adverse Events of Special Interest

The following adverse events of special interest will be monitored during the study:

- Headache
- Visual disturbance

Subjects reporting a headache AE (including any AE related to headache or migraine) will be provided the supplemental headache AE assessment form to further assess the headache AE and grade the degree of severity.

Adverse Event Severity and Relationship to Study Drug

The investigators will rate the severity of each AE as mild, moderate, or severe.

The investigator will use the following definitions to rate the severity of each AE:

Mild	The adverse event is transient and easily tolerated by the subject.
Moderate	The adverse event causes the subject discomfort and interrupts the subject's usual activities.
Severe	The adverse event causes considerable interference with the subject's usual activities and may be incapacitating or life threatening.

The investigator will use the following definitions to assess the relationship of the AE to the use of study drug:

Reasonable Possibility	After consideration of factors including timing of the event, biologic plausibility, clinical judgment, and potential alternative causes, there is sufficient evidence (information) to suggest a causal relationship.
No Reasonable Possibility	After consideration of factors including timing of the event, biologic plausibility, clinical judgment, and potential alternative causes, there is insufficient evidence (information) to suggest a causal relationship.

Pregnancy

While not an AE, pregnancy in a study subject must be reported to AbbVie within 24 hours after the site becomes aware of the pregnancy. Subjects who become pregnant during the study must be discontinued (Section 5.5). If a pregnancy occurs in a study subject or in the partner of a study subject, information regarding the pregnancy and the outcome will be collected.

The pregnancy outcome of an elective or spontaneous abortion, stillbirth, or congenital anomaly is considered an SAE and must be reported to AbbVie within 24 hours after the site becomes aware of the event.

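### Two of the six SAE criteria are worded around a drug: the life-threatening row literally omits events averted by a procedure, and the important-medical-event row is garbled.

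*Protocol*

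**What the plan says.** Protocol Section 6.1 lists six criteria for a serious adverse event. Meeting any one of them obliges the site to report the event as a "Serious adverse event (SAE) within 24 hours of the site being made aware of the SAE".

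Two of the six mention a drug as the thing that averts the bad outcome:

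- Life-threatening: in the investigator's opinion the event "would have resulted in immediate fatality if medical drug had not been taken".
- Important medical event: the row is headed "Important Medical Event Requiring Medical or Surgical Drug to Prevent Serious Outcome", and its text covers an event that, on medical judgment, "may jeopardize the subject and may require medical or surgical drug to prevent any of the outcomes listed above".

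The rule in the same section on when a vital-sign change counts as an AE has similar wording. One trigger is that the change should "necessitate therapeutic medical drug, and/or if the investigator considers them to be AEs".

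The other four criteria (death, hospitalization, congenital anomaly, disability) say nothing about how the event was treated. Hospitalization, for instance, is "An event that results in an admission to the hospital for any length of time" or one that prolongs a stay, but emergency-room visits and outpatient-facility admissions are expressly left out.

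**The concern.** A seriousness criterion normally asks what would have happened without treatment of any kind. Here one criterion asks only whether a drug was taken, and another refers to a surgical drug, which does not exist. A site following the text closely could decide that an event controlled by a procedure does not qualify.

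Other parts of the plan depend on these rows. They trigger the 24-hour report in Protocol Section 6.1 and Operations Manual Section 4.2. The SAR and SUSAR definitions in Section 6.1 refer back to them. Protocol Section 7.6 defines a treatment-emergent SAE as a TEAE that meets one of the SAE criteria, and that definition feeds the serious TEAE lines in SAP Section 10.2.2 (ocular and nonocular) and the SAE tables and listings in SAP Section 10.2.4. An event not flagged as serious is absent from all of these.

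**Working it through.** No arithmetic applies. The check is whether the wording excludes procedures, whether anything corrects it, and what the remaining criteria still capture.

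**Step 1: the wording.** Of six criteria, two contain the drug wording and 6 − 2 = 4 do not.

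- The life-threatening row names only a medical drug. It cannot easily be stretched to procedures, because the paragraph on elective surgery just above it uses surgery and procedure as separate terms.
- The important-medical-event row pairs *medical* with *surgical*. The noun is wrong, but surgery is mentioned. The row turns on medical judgment, asks only whether treatment may be required, and gives examples that do not depend on a drug: "allergic bronchospasm requiring intensive treatment in an emergency room or at home" and "blood dyscrasias or convulsions that do not result in inpatient hospitalization".

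**Step 2: is it corrected elsewhere?** Operations Manual Sections 4.1 and 4.2 repeat the collection and reporting duties without redefining an SAE. SAP Section 10.2 uses the term without a definition. Nothing in the available text repairs the wording. One caveat: Protocol Section 6.1 sends sites to Operations Manual Section 4.3 for reporting details. That section does not appear in the available text, where the reporting instructions stand in Section 4.2.

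**Step 3: what is still captured.**

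| Event | Criterion that applies | Does the drug wording matter? |
|---|---|---|
| Ends in death | Death | No |
| Procedure with hospital admission | Hospitalization | No |
| Leaves substantial interference with daily activities | Disability | No |
| Would have been immediately fatal; averted by a drug in an emergency room | Life-threatening | No, the row is met |
| Would have been immediately fatal; averted by a procedure in an emergency room or outpatient setting | Life-threatening fails literally; important medical event if read to include surgery or on judgment | Yes |
| May jeopardize the subject; managed by an outpatient procedure | Important medical event, if read to include surgery or on judgment | Yes |

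Only the last two lines depend on the defective text, and both can still be reported through the important-medical-event row by a site that reads it sensibly.

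**Step 4: what is lost if a site reads it narrowly.** All AEs are collected from study drug administration to study exit (Protocol Section 6.1, Operations Manual Section 4.1), TEAEs are tabulated and all AEs are listed (Protocol Section 7.6). The event stays in the database. It loses its seriousness flag, its 24-hour report and its place in the serious TEAE counts.

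**Step 5: the vital-sign rule.** It ends with an alternative that makes any change an AE if the investigator considers it one. The wording is faulty but has little effect.

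**Step 6: likely cause.** Operations Manual Section 2.1 still speaks of study intervention where the protocol body says study drug. Protocol Section 7.8 sizes the trial per study drug group where SAP Section 2.4 says per study treatment group. This pattern, and the meaningless phrase itself, suggest that *intervention* was replaced by *drug* in bulk. That is an inference: the documents do not say so, and the Operations Manual itself uses both terms.

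**The case against.** The strongest reply is that this is a typing error that no clinician would act on. The important-medical-event row says *surgical*, relies on judgment and lists examples without a drug condition. Death, admission and disability are covered independently. What is left is a narrow class of events, improbable in a 14-day eye-drop trial in adults aged 40 to 55. Most of this stands and sets the limits of the point. It does not dispose of it: the life-threatening row really is too narrow as written, and nothing available corrects it.

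Three stronger readings are tempting, and the documents do not support them.

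- A reader might infer that every event averted by surgery falls outside the SAE definition. It does not. The important-medical-event row mentions surgery, and any admission qualifies by itself.
- A reader might infer that a retinal tear or detachment found at the exit examination (Operations Manual Section 3.22) and treated as an outpatient would be missed. Unless it led to disability or admission, it would depend on the important-medical-event row. That row names surgical treatment and allows judgment, so it can capture the event. That such events are treated as outpatients is a clinical assumption, not a statement in the documents.
- A reader might assume an SAE rate of 0.5% to 1%, obtain 200 × 0.5% = 1 to 200 × 1% = 2 expected SAEs, and conclude that one missed event removes half or all of the signal. The rate has no source in the documents, and the calculation presupposes the miss instead of estimating its probability.

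**Conclusion.** The defect is real and uncorrected in the text available, and it sits in operative text. The life-threatening criterion literally omits events averted by a procedure. The important-medical-event heading and text are garbled and open to inconsistent reading across about 20 sites, though most would probably still include surgery. The exposure is limited to events managed by a procedure in an emergency room or outpatient setting. Its consequence is a possible missing seriousness flag, 24-hour report and serious TEAE count, not a missing AE. No numerical magnitude can be derived from the documents. Efficacy analyses, sample size, power and Type I error are unaffected. The conclusion assumes that no part of the plan outside the available text restates the criteria.

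**What to change.** In the next amendment, reword the life-threatening row and both the heading and the text of the important-medical-event row in Protocol Section 6.1, so that they cover medical or surgical intervention and not only a drug. Correct the parallel phrase in the vital-sign rule for consistency, and search the protocol for other instances of the same substitution. Tell the sites how the criteria are to be read. The same communication can confirm which Operations Manual section holds the SAE reporting instructions.

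The cost is four small wording changes and one site communication. No endpoint, analysis, dose or visit procedure changes.
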